## 1 List of Abbreviations

Abbreviation	Abbreviation definition
SUD	Substance use disorder
SMD	Severe mood dysregulation
DMDD	Disruptive mood dysregulation disorder
SGA	Second Generation antipsychotic
BD	Bipolar Disorder
M.I.N.I 7.0	Mini-International Neuropsychiatric Interview
KSADS-PL	DMS-V Kiddie Schedule for Affective Disorders and Schizophrenia Present and Lifetime
YMRS	Young Mania Rating Scale
AIMS	Abnormal Involuntary Movement Scale
CGI	Clinical Global Impressions
C-SSRS	Columbia Suicide Severity Rating Scale
GAF	DSM-V Global Assessment of Functioning
ASR	Adult Self-Report
YSR	Youth Self-Report
BRIEF	Behavior Rating Inventory of Executive Function
BDI-II	Beck Depression Inventory-II
PHQ-9	Patient Health Questionnaire-9
TLFB	Timeline Followback of Substance Use
AE	Adverse event
SAE	Serious adverse event

## 2 Protocol Summary

Title:	A Randomized Controlled Trial of Quetiapine for the Treatment of Youth With Co-Occurring Substance Use Disorders (SUDs) and Severe Mood Dysregulation (SMD)
Population:	We plan to enroll 56 youth, ages 15 to 24, with SUD and SMD.
Intervention:	Drug name: Quetiapine Route of administration: Oral Dose: Quetiapine will be titrated to the maximum achieved dose as tolerated during the first three weeks of the trial. Study medication will be initiated at 50 mg twice daily and will be gradually up-titrated by 100 mg per day (increasing by 50 mg twice daily) to a maximum dose of 150 mg twice daily. Titration of the study medication is flexible, guided by tolerability with the option for slower, lower, or hold titration. If a participant prefers once daily dosing instead of twice daily dosing this will be allowed.
Objectives:	Specific Aim 1: To evaluate the effect of quetiapine on SUD in youth with SUD and SMD

**Specific Aim 2:** To evaluate the effect of quetiapine on SMD in youth with SUD and SMD.

**Specific Aim 3:** To evaluate the effect of quetiapine on engagement in outpatient treatment in youth with SMD and SUD.

**Specific Aim 4:** Assess the safety and tolerability of quetiapine in youth with SUD and SMD.

**Exploratory Aims:** Evaluate whether substance use and mood symptoms are related and if so, examine the nature of the relationship. Evaluate whether scales that measure emotional regulation, the Emotional Control Subscale for the Behavior Rating Inventory of Executive Function and the Anxiety/Depression, Attention, and Aggression subscales of the Youth Self-Report or Adult Self-Report, predict treatment response and/or what specific components improve with treatment. Evaluate whether the Patient Health Questionnaire-9 is a valid measure of mood symptoms in youth with co-occurring substance use and SMD. Examine the impact of quetiapine (versus placebo) on self-reported and objective measures of non-primary substances of use. Evaluate whether differences exist in medication adherence, high-risk behaviors associated with HIV and Hepatitis C, and global functioning between the active treatment and placebo groups. Examine the impact of common psychiatric co-morbidities for youth with SUD and SMD on outcome and retention in the study. Evaluate whether youth's reasons for substance use, motivation to change, and confidence in their ability to change impact response to treatment. Assess whether level of engagement in self help and therapy impact response to treatment. Evaluate whether peer substance use and exposure to substance use in the subject's living environment impact response to treatment.

Design/Methodology:	To evaluate the effect of quetiapine on substance use, SMD, and engagement in care, we are proposing an 8-week randomized, double blind placebo controlled parallel design study for youth with SUD and SMD who are entering into or currently engaged in behavioral therapy. Please refer to the Schedule of Events in the Appendix for a table of visits and assessments.
Total Study Duration:	Open for Data Analysis until May 2022

---

**Subject Participation Duration:** 10 weeks

---

### 3 Background/Rationale & Purpose

#### 3.1 Background Information

Substance use disorders (SUDs) in youth commonly co-occur with categorical and dimensional measures of psychopathology [1-4] including prominent dysregulation of mood and emotions found in severe mood dysregulation (SMD). For clarity in this project, SMD includes bipolar spectrum disorders, disruptive mood dysregulation disorder, and mood disorder not otherwise specified. While a growing literature suggests an important link between SMD and SUD [5] the relationship between SMD and SUDs has been best characterized in youth with SMD indicative of bipolar disorder (BD). Specifically, among adolescents with SUD, 8% to 32% have been found to have BD. [1, 6-8] Conversely, clinical samples of adolescents with BD also have elevated rates of SUD, ranging from 9% to 39% when evaluated cross-sectionally and followed prospectively.[9-14]

SUD co-occurring with SMD is particularly concerning due to the morbidity associated with the co-occurrence of both disorders. For example, in BD we found that young people (mean age 21 years) with co-occurring SUD and BD had significantly higher rates of severe SUDs (13% had an opioid use disorder and 9% a cocaine use disorder) compared to similar aged non-mood disordered control peers.[15] Co-occurring SUD and BD in youth has also been associated with increased morbidity when compared to youth with BD alone. Compared to BD alone, youth with SUD and BD have higher rates of lifetime hospitalizations[15], increased lifetime prevalence of suicide attempts, and higher rates of past year legal difficulties, and more frequent unplanned pregnancies and abortions among females.[16] Delbello and colleagues [11] found that none of the adolescents with BD, attention deficit hyperactivity disorder (ADHD), and alcohol use disorder were adherent with medication during the year following hospitalization for a manic episode compared to 38% in similarly affected adolescents without an alcohol use disorder. Medication nonadherence was associated with a longer recovery period after initial hospitalization in this same sample of adolescents with BD.[11]

Although less studied, evidence exists that SMD, such as observed in BD, may be driving SUD in some youth.[5, 17-19] For example, in a case controlled sample of BD, we reported that emotional dysregulation was significantly linked with an increased risk for SUD.[5] Lorberg and colleagues found that adolescents with BD and SUD were more likely than controls with SUD to start using their drug of choice to change their mood[18] Additionally, Goldstein and colleagues in a longitudinal sample of BD spectrum youth found a strong relationship between mood symptoms and substance use.[17] In adolescents with BD greater hypo/mania symptom severity was observed in the 12 weeks before they developed a SUD compared to other 12 week periods over four year follow up and compared to adolescents with BD who did not develop a SUD. Since SMD may be associated with substance use it follows that treatments developed for SMD may be effective in reducing substance use in youth with co-

occurring SUD and SMD.

Despite the high prevalence and morbidity associated with SUDs and SMD in youth, there is a dearth of studies on the treatment of this comorbidity. Only one small randomized control trial (RCT) of lithium in SUD adolescents with or at high risk for BD (e.g. SMD) has been published. [20] In this study twenty-five adolescents were randomized to lithium with mean blood levels 0.9 mEq/L versus placebo and followed twice weekly during the six week trial. Adolescents treated with lithium had significant improvement in their SUD and overall improved functioning compared to controls.[20] Interestingly, no change in mood scores was observed, and despite a strong signal in a relatively small sample that treatment with a mood stabilizer leads to a reduction in substance use in adolescents with co-occurring SUD and SMD, no other medication RCTs have been published in this high-risk group.

Lithium's usefulness for the treatment of youth with SUDs and SMD has been limited due to lithium's narrow therapeutic index and concern regarding toxicity in patients with active substance use due to associated shifts in hydration and adherence to monitoring.[21, 22] Since Geller's publication a new class of mood stabilizers, second generation antipsychotic (SGAs) medication, have been developed that appear to have less risk for acute toxicity. A significant literature supports the effectiveness of SGAs for the treatment of SMD, specifically adolescent manic symptoms and DMDD.[23-26] A recent meta-analysis suggested superior efficacy of SGAs for mania in adolescents compared to traditional mood stabilizers.[24] Several SGAs have FDA approval for use in adolescents with manic episodes associated with BD including: risperidone, olanzapine, quetiapine, and aripiprazole.[27] Furthermore, adolescent versus adult-onset manic symptoms appear more responsive to SGAs than traditional mood stabilizers.[28] Less information exists on the effectiveness of SGAs for the treatment of depressive symptoms in youth with BD. [29] Given the efficacy associated with SGAs for SMD it is no surprise that SGAs are increasingly used in the treatment of SMD.[30, 31]

Since excess dopamine is thought to mediate the reinforcing effect of substances of abuse in the reward circuitry system of the brain[32] dopamine antagonists and SGAs in particular have been investigated as a treatment for SUDs in adults. Positive findings have been found for olanzapine, aripiprazole and quetiapine for various measures associated with substance use in adults with SUDs. Both one dose of olanzapine and five days of daily olanzapine were shown to be effective in decreasing alcohol cravings when subjects were exposed to alcohol.[33, 34] Further work by Hutchinson et al in a 12-week RCT demonstrated olanzapine to be effective for decreasing cravings for alcohol and alcohol consumption in subjects with alcohol dependence who had a particular genetic polymorphism.[35] Aripiprazole was evaluated as a treatment for adults with alcohol dependence in a 12-week RCT.[36] While there was no difference between aripiprazole and placebo in percent days abstinent, the aripiprazole group reported significantly fewer drinks per drinking day and subjective improvement in their alcohol dependence.[36] In contrast, several RCTs of both olanzapine and risperidone did not show superior efficacy to placebo in decreasing cravings for cocaine[37-39] or cocaine use[37, 38, 40] in adults with cocaine use disorders. Open label treatment with quetiapine however was shown to be effective in decreasing cravings for

cocaine and days of cocaine use.[41] A retrospective review of males with alcohol dependence who were treated or not treated with quetiapine demonstrated treatment with quetiapine was associated with increased number of days abstinent and decreased number of hospitalizations.[42] Another retrospective review of patients with opioid use disorders engaged in outpatient opioid detoxification found that quetiapine was associated with decreased opioid cravings in 74% of patients.[43] Hence, the preponderance of data seems to suggest a role for SGAs in SUD; however, little is known about this treatment in youth with SUD.

Research on the efficacy of SGA medication in RCTs for the treatment of adults with co-occurring SUD and a type of SMD, BD, has been mixed. Quetiapine, approved by the FDA for both manic and depressive episodes associated with adult BD, has been the most extensively studied SGA for the treatment of adults with co-occurring SUD and BD. When compared to placebo as adjuvant treatment, quetiapine significantly decreased alcohol use and depressive symptoms in a subgroup of adult patients with heavy baseline levels of alcohol consumption who met criteria for an alcohol use disorder and BD.[44] Both quetiapine and risperidone were equally effective in improving mania, mixed, and depressive symptoms as well as drug cravings when compared in a RCT trial for the treatment of adults with co-occurring stimulant use disorders and BD.[45] An open label study of quetiapine for cocaine dependence and BD showed improvements in cravings for cocaine and measures of mood, with nonsignificant decreases in days per week of cocaine use.[46] Other studies that evaluated quetiapine as adjuvant medication and the primary medication for the treatment of co-occurring alcohol dependence and BD did not find significant differences between placebo.[47, 48] Although treatment trials of adults with co-occurring SUD and BD provide some guidance on effective treatment strategies it is unclear if youth with co-occurring SUD and SMD would respond similarly to adults based on the different phenotypic descriptions of BD and medication treatment responses seen between youth and adults with BD.

To our knowledge there have been no published papers to date specifically examining treatment of co-occurring SUD and SMD in youth with SGAs. Delbello reported on a RCT in adolescents with frequent cannabis use and BD with symptoms of mania (Young Mania Rating Scale (YMRS) score greater than 20) who were treated with quetiapine and randomized to topiramate or placebo.[49] Although quetiapine plus topiramate was more effective than quetiapine alone in reducing substance use, both treatment groups showed overall improvement in substance use and mood. Substance use decreased by 10 joints per week (-72%) in the quetiapine only group and by 10.6 joints per week (-96%) in the quetiapine plus topiramate group. YMRS scores decreased by 16 in the quetiapine only group (ca -53%) and 14 (ca -47%) in the quetiapine plus topiramate group—these data suggest quetiapine could be a highly useful intervention for treatment of SUD co-occurring with BD when adolescents are experiencing symptoms of mania. Further research is warranted to determine if quetiapine would be more efficacious compared to placebo in decreasing both SUD and affective symptoms.

To this end, we aim to study the efficacy of a SGA, quetiapine, as treatment for active SUD, as well as

mood symptoms in youth with SUD and SMD in a naturalistic, outpatient treatment setting. Quetiapine was selected as the SGA to target SUD and SMD since the adolescent and adult literature has suggested possible efficacy for treatment of SUDs and quetiapine is FDA approved for the treatment of adolescent BD.

We propose to use quetiapine as an adjunct treatment to treatment as usual to improve both SUD and mood symptoms in a double blind, parallel design RCT over 8 weeks for youth with SUD and SMD who are in a comprehensive outpatient treatment program utilizing evidence based family and individual behavioral therapies.[50, 51] Our trial will examine a number of important variables including the impact of acute treatment with quetiapine on SUD, mood, and treatment engagement in youth with co-occurring SUD and SMD. Although this study cannot directly evaluate the relationship between substance use and mood symptoms and vice versa, we will closely monitor the trajectory of these symptoms. We will also explore whether scales that measure SMD—the Emotional Control Subscale for the Behavior Rating Inventory of Executive Function (BRIEF)[52] and the Anxiety/Depression, Attention, and Aggression (AAA) subscales of the Youth Self-report (YSR)[53] or Adult Self-Report (ASR)[54], which are self-report versions of Achenbach System of Empirically Based Assessments based on age—predict treatment response in youth with co-occurring SUD and SMD; as well as specific improvement in areas thereof that may be reflective of improved SUD. We will explore the impact of quetiapine (versus placebo) on self-reported and objective measures of non-primary substances of use. We also plan on exploring the impact of pharmacologic treatment on medication adherence, retention in treatment, high-risk behaviors associated with human immunodeficiency virus (HIV) and hepatitis C virus (HCV), and overall global functioning. Furthermore, we will examine the impact of common psychiatric comorbidities for youth with SUD and SMD, such as conduct disorder, attention deficit hyperactivity disorder (ADHD), and anxiety, on outcome and retention in the study.

As noted earlier, quetiapine is FDA approved for the treatment manic episodes associated with bipolar disorder in adolescents, and the treatment of manic and depressive episodes associated with bipolar disorder in adults. An IND was not requested because this study is not intended to support a new indication for use, change in labeling for the drug, or change in the advertising of quetiapine. Furthermore, this study does not involve a change in route of administration or dosage level, use in a subject population, or other factor that significantly increases the risk associated with the use of quetiapine.

This study was originally approved by the Partners Healthcare IRB on 09/14/2016 and has been taking place at the Massachusetts General Hospital (MGH). To date the study has completed 161 phone screens, scheduled 75 screening visits, consented 39 subjects, and randomized 19 subjects. Since the PI has changed employers from MGH to BMC this study is currently closed to recruitment at MGH and is being closed with the Partners IRB.

This study will be conducted in compliance with the protocol, applicable regulatory requirements, and BMC/BU Medical Campus Human Research Protection policies and procedures.

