Before receiving study medication, the healthy lifestyle behavior recommendations developed by Correll and Carlson to prevent and minimize weight gain on SGAs will be reviewed with all eligible subjects. Participating youth with active SUD and SMD will be randomized to treatment or placebo in a 1:1 ratio. Randomization lists will be generated by the investigational pharmacy for each age block (e.g. 15-17; 18-24 years). Throughout the 10-week study participants will be encouraged to engage in treatment as usual which includes evidence based behavioral therapies through the Center for Addiction Treatment for Adolescents/ Young Adults who use Substances (CATALYST) at Boston Medical Center.

Subjects will be sent appointment reminders via text before their study visits. Reminders will be sent from a cell phone designated for this study's purposes and will only contain the date, time, and location of the appointment. No personal/health information will be shared over text.

The collection of certain scales and study procedures will occur at all 11 visits, and include the following:

Clinician rated assessments:

- Mini-International Neuropsychiatric Interview (M.I.N.I. 7.0)[57]: The M.I.N.I is a short, structured, diagnostic interview with an administration time of approximately 15 minutes that is the structured interview of choice for psychiatric outcome tracking in clinical psychopharmacology trials. Specific, predetermined modules will be completed to assess for DSM-V mood disorders, disruptive disorders, SUDs and anxiety disorders (will be administered at screening). The suicidality, lifetime panic disorder and optional assessment measures to track changes over time including cross cutting measures and disability/functional impairment will not be utilized in the study. The M.I.N.I KID will be administered in subjects under the age of 18. In these interviews the suicidality, separation anxiety disorder, Tourette's disorder, adjustment disorder and autism spectrum disorder modules will also not be utilized in the study.

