## 11 Data Handling and Record Keeping

### 11.1 Confidentiality

All research related records initiated as a result of a subject's participation in this study that reveal the subject's identity will remain confidential except as may be required by law. Data obtained from this study will not identify the subjects individually. Subjects will be assigned code names and ID numbers. Biospecimens will be stored securely in a locked room only accessible to study staff. Data obtained from our studies may be published, but published data will not identify individual participants. Original research-related records may be reviewed by the Boston Medical Center Institutional Review Board and regulatory authorities for the purpose of verifying clinical trial procedures and/or data. Information will be held and processed on a computer, but access to these computerized records will be password protected and restricted to study staff. At the onset of an initial clinical encounter, subjects will be informed of Federal privacy guidelines that pertain to them under the Healthcare Insurance Portability and Accountability Act. Results of urine drug or pregnancy testing will not become part of the subject's medical record. Subjects will only be contacted regarding future studies if they indicate that they are

interested in being contacted by initialing in the specific section of the consent form. Information may be held and processed on a computer. Access to these computerized records will be password protected and restricted to study staff.

Data Use Agreements and Material Transfer agreements will be filed with the appropriate offices regarding receiving identified data and biospecimens from Massachusetts General Hospital.

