#### 12.2 Sample Size Determination

Since there have not been any published studies to date on quetiapine for the treatment of SUD co-

occurring with SMD in young people, we are estimating the effect size of quetiapine for the treatment of youth with co-occurring SUD and SMD based on Delbello and colleagues' preliminary report on a sample of 75 patients with frequent cannabis use and BD who were treated with quetiapine and randomized to topiramate or placebo.[49] The quetiapine plus placebo group had improvements in both substance use and mood. Cannabis use decreased from an average of 14 joints per week to 4 joints per week representing a 72% decrease. In this study, the YMRS decreased by 16 (from approximately 30 to 14) indicating a 53% improvement in mood. These expected improvements in SUD associated with mood are reminiscent of those of Geller et al using lithium for youth with SUD and SMD (effect size of ca 1.0). [20]

**Power Analysis:** To achieve 90% power using a two-tailed test with 5% significance level to detect a difference in measures of substance use we will need 22 subjects per group. To detect similarly powered differences in measures of mood we will need 10 subjects per group. Clinical trials for quetiapine in adolescents with BD have a 75 to 80% completion rate.[71, 72] We therefore estimate we may have 20% attrition and aim to recruit 28 subjects per group for a total of 56 subjects.

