### 12.3 Statistical Methods

All analyses will be modified intention to treat, which will be defined by completing at least one week of study medication. We will analyze group differences across demographics using Pearson's Chi Squared tests for binary outcomes and student t tests or linear regression models for continuous outcomes. To assess our main outcomes, we will use generalized estimating equations that estimate the main effects of drug and time as well as any interactions (time X drug). We will evaluate our primary outcome measures hierarchically in the following order for SUD: Timeline Followback of substance use, urine drug screen, and Weiss craving scale. For binary outcomes, logistic regression models will be fit with Poisson family and log link, and for normally distributed data, linear regression models will be fit with the Gaussian distribution and the identity link. Exploratory aims will be examined using models similar to the main outcomes. All statistical tests will be performed using STATA 13.0. The statistical significance will be set at 5% and all tests will be two-tailed.

To evaluate hypotheses 1A, 1B and 1C, we will monitor SUD response to quetiapine for primary substance of use by way of the Timeline Followback of Substance Use (TLFB). Specifically, the TLFB will be used to compare self-report of substance for the month prior to study entry versus the last month of the study. We will use weekly toxicology screens negative for primary substance of abuse as an objective measurement of decrease in substance use severity. The Weiss Craving Scale will be used to assess the effect of quetiapine treatment on cravings for primary substance of use. Values for all three measures (TLFB, toxicology screens, and Weiss Craving Scale) will be compared between baseline and endpoint.

To evaluate hypotheses 2A and 2B, we will assess SMD response to quetiapine by way of comparing

values from baseline to endpoint on the YMRS and BDI-II.

To evaluate hypothesis 3A, the impact of treatment with quetiapine on outpatient treatment engagement will be monitored by collateral from the outpatient program regarding the percentage of scheduled appointments attended after randomization.

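### The 19 participants randomised at the first hospital appear set to be pooled with those from the second, but the outcome models have no hospital term, which costs some precision, most clearly for attendance (3A)

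*Combined protocol and SAP*

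**What the plan says.** - **History.** Section 3.1 says the trial had "consented 39 subjects, and randomized 19 subjects" at the first hospital (MGH), and that "this study is currently closed to recruitment at MGH". Everyone randomised later therefore comes from the second hospital (BMC).
- **Pooling.** Section 11.1 foresees agreements for "receiving identified data and biospecimens from Massachusetts General Hospital". The target is unchanged: "We plan to enroll 56 youth, ages 15 to 24, with SUD and SMD" (section 2), and 12.2 still arrives at 56. No section says outright that the 19 are part of the 56.
- **Randomisation.** Section 9.3: "Randomization lists will be generated by the investigational pharmacy for each age block". Age is the only stratification factor named. Nothing says whether new lists began at the move or the existing ones continued.
- **Background care.** Section 9.3 says usual care includes "evidence based behavioral therapies through the Center for Addiction Treatment for Adolescents/ Young Adults who use Substances (CATALYST) at Boston Medical Center". Care at the first hospital is not described, and section 8 names only the second hospital's research pharmacy.
- **Analysis.** Section 12.3 specifies "generalized estimating equations that estimate the main effects of drug and time as well as any interactions (time X drug"). Hospital is not in the model.

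**The concern.** Quetiapine is tested as an addition to usual care, so the setting acts on both arms. Hospital is also tied to calendar period, and the current protocol allows virtual visits (5.1) with self-administered urine drug tests (9.3). How the first 19 were followed is not described, but it may have differed.

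If outcomes differ between hospitals, a model without a hospital term handles the difference in one of two ways. Where arms are balanced within hospital, the difference inflates the residual variance, so standard errors are too large. Where they are not balanced, part of it moves the estimated drug effect in a random direction.

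Exposure differs by outcome. Hypothesis 3A uses the share of scheduled appointments kept after randomisation, as reported by the treatment programme. It has no baseline value, so a hospital difference enters in full. For Aims 1 and 2 the drug × time term largely cancels a constant difference in level, and only a different rate of change between hospitals matters.

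**Working it through.** **1. The plan's own figure.** Inputs from 12.2: 90% power, "using a two-tailed test with 5% significance level", an effect size of about 1.0, 20% attrition.

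- n per arm = 2(1.960 + 1.282)² / 1.0² = 21.0, rounded up to 22. The t-test version gives 22.02, and t-test power at 22 per arm is 90.0%.
- 22 / 0.80 = 27.5, rounded up to 28 per arm, 56 in total. The plan's figures reproduce.

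**2. Variance added by leaving hospital out.** Let p be the share from the first hospital and s the difference between hospitals, in within-hospital SDs of the outcome (3A) or of its change (Aims 1 and 2).

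- If the 19 are pooled, p = 19/56 = 0.339, leaving 56 − 19 = 37 for the second hospital; p(1 − p) = 0.224.
- Variance ratio V = 1 + 0.224 s². Equivalent sample loss = 1 − 1/V.
- Power is that of a two-sample t-test with 22 per arm and effect 1.0/√V.

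The documents give no value for s, so 0.2 to 1.0 is an assumption.

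| s (SD) | V | Equivalent sample loss | Power without hospital term |
|---|---|---|---|
| 0.2 | 1.009 | 0.9% | 89.7% |
| 0.5 | 1.056 | 5.3% | 88.4% |
| 1.0 | 1.224 | 18.3% | 83.4% |

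To recover 90% power without the term, the total would need to be 56, 58 and 66 respectively.

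**3. Type I error.** If arms are balanced within hospital, the drug estimate does not carry the hospital difference but the unadjusted standard error does. Realised two-sided level = 2[1 − Φ(1.96√V)].

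- s = 0.5: 1.96 × 1.028 = 2.014, giving 4.4%.
- s = 1.0: 1.96 × 1.106 = 2.169, giving 3.0%.

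**4. Simulation check.** Linear models with 44 evaluable participants (15 and 29 by hospital), 5,000 runs per scenario:

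- The mean estimate stayed at its true value (0 or 1.0) with or without the term, so there is no systematic bias.
- Without balance within hospital, the unadjusted test held about 5%. With balance, it rejected in 4.8% of null runs at s = 0.5, 4.1% at 0.8 and 2.9% at 1.0. The value at 0.5 is within simulation error of the 4.4% in step 3.
- With the term, power was about 89% to 90% at every s from 0.3 to 1.0.

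**5. Chance imbalance, if lists did not balance within hospital.** With 28 per arm, a split of the 19 as uneven as 12:7 has probability 26%, and 13:6 has 9%. A 13:6 split shifts the estimate by (13 − 6)/28 × s = 0.25s, which is 0.05, 0.125 and 0.25 SD at s = 0.2, 0.5 and 1.0. The standard error is √(2/22) = 0.30 SD.

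With separate 1:1 lists the shift is smaller. For example, take 11:8 at the first hospital and 18:19 or 19:18 at the second. The imbalance is 11/29 − 8/27 = 0.083 or 11/30 − 8/26 = 0.059, so the shift is about 0.03 to 0.08 SD for s of 0.5 to 1.0.

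**The case against.** The strongest reply is that no validity is lost. Randomisation removes systematic bias, and the unadjusted test is at or below its nominal level. Up to 0.5 SD the power loss is under 2 percentage points, and a difference of 1.0 SD would be as large as the drug effect cited in 12.2. All of this stands, and it makes the point one of efficiency.

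Three stronger readings are tempting, and the documents do not support them:

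- **That the hospitals used different care programmes and pharmacies.** This is plausible because the named programme and pharmacy belong to the second hospital, but those at the first are never described.
- **That randomisation was separate by hospital.** Section 9.3 does not say how the lists were handled at the move, so both the balanced and the unbalanced case have to be shown.
- **That hospital measures background care, which the plan ignores.** Usual care only includes the named programme, and 9.1 also recruits from psychiatry clinics, another study, schools and social media. Care can therefore vary within the second hospital, and a hospital indicator is a rough proxy for it. The plan does examine engagement in therapy as an exploratory aim, though that does not replace a hospital term.

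Pooling itself is implied and not stated. If the 19 are not pooled, the point falls away.

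**Conclusion.** The concern holds as a modest loss of precision. Hospital is known for every participant, the first hospital would supply about a third of a small sample, and 12.3 leaves it out. Over an assumed difference of 0.2 to 1.0 SD, variance rises by about 1% to 22% and power falls from about 90% to between 89.7% and 83.4%. The test is also conservative if arms are balanced within hospital.

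A reader might infer a biased drug effect or an inflated false-positive rate. Neither follows: any shift is by chance and has mean zero over randomisations.

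The size rests on the assumed difference, on pooling of the 19, and on a two-sample comparison standing in for the generalized estimating equations. 3A is the clearest case. For Aims 1 and 2 the loss arises only if the rate of change differs between hospitals.

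**What to change.** Before unblinding:

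1. State in 12.2 and 12.3 that the 19 participants from the first hospital are pooled and count toward the 56.
2. In 12.3, add a hospital main effect to the 3A model.
3. For Aims 1 and 2, add hospital to the models. Include hospital × time only where time is coded as baseline versus endpoint or as linear. Alternatively, model the endpoint adjusted for its baseline value, plus hospital. A main effect alone does little for the drug × time test, because it removes level and not change.

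**Cost.** This needs only analysis-plan wording and no new data. It uses one degree of freedom for 3A and one or two for Aims 1 and 2 under the coding above. Section 12.3 does not say how time is coded. With categorical time, hospital plus hospital × time would take 1 + 4 = 5 parameters for scales given at week 0 and every two weeks to week 8, and 1 + 8 = 9 for a measure taken weekly from week 0 to week 8. That is heavy for about 44 evaluable participants, which is why the interaction should be limited to simple time coding.
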